4.2 Pharmacokinetic Studies

PK studies will be conducted on CSF from each lumbar puncture performed during the study and on selected plasma specimens. Timing of blood and CSF collections will be recorded. For a subset of participants, we will do a more intensive plasma sampling regimen by collecting multiple peripheral blood samples after the first dose of 5-FC that day.

In Kampala, cell pellets of CSF white cells and peripheral blood mononuclear cells (PBMCs) will be collected for potential immunologic studies.

4.3 Antifungal Susceptibility Testing

Minimum inhibitory concentration (MIC) testing will be performed on all participants in the investigational cohort with *Cryptococcal* growth on CSF culture. Broth microdilution, as recommended by the European Committee on Antimicrobial Susceptibility Testing will be used to determine the MIC.

5. STUDY ENROLLMENT AND WITHDRAWAL

5.1 Inclusion Criteria

- CSF cryptococcal antigen (CrAg) positive meningitis
- Ability and willingness to provide informed consent
- Willing to receive protocol-specified lumbar punctures

Exclusion Criteria

- Age < 18 years
- Inability to take enteral (oral or nasogastric) medicine
- Cannot or unlikely to attend regular clinic visits
- Receiving chemotherapy or corticosteroids
- Suspected paradoxical immune reconstitution inflammatory syndrome (IRIS)
- Pregnancy or breastfeeding (tested on screening)
- CrCl < 20 mL/minute*
- Absolute neutrophil count < 500 x 10⁶ cells/L*
- Thrombocytopenia < 50,000 x 10⁶ cells/L*
- Patients with prior 5-flucytosine exposure ≥3 days in the 12 months prior to enrollment
- Any condition for which participation would not be in the best interest of the participant or that could limit protocol specified assessments.

Rationale for Phase II Trial Criteria

The inclusion and exclusion criteria of the Phase II trial are meant to be broad to enroll a representative sample of persons in resource-limited areas, and thereby be broadly generalizable. Flucytosine and fluconazole are known teratogens in the first trimester. Amphotericin is the preferred drug of choice during pregnancy. Since therapy includes flucytosine or fluconazole, pregnant and breastfeeding women are excluded.

Other exclusion criteria are intended to minimize bias and maximize likelihood of completing the study or need to customize therapy (e.g., pregnant women).

Note on subjects with positive CSF CrAg but subsequent negative CSF cultures:

Since CSF CrAg is more sensitive than CSF culture in very early disease with a low fungal burden,^{18,54} CSF culture-negative patients with a positive CSF CrAg will be assumed to have early CM and be eligible for the study and included in the analyses. Approximately 10-15% of participants are estimated to be culture negative. CSF cultures take 7-14 days for results, thus are not a realistic criterion for enrollment as therapy is initiated based on CSF CrAg results. CSF

CrAg LFA is markedly more sensitive than India ink microscopy.⁵⁴ Although these participants will not contribute to the quantitative CSF clearance data, they will contribute to all other endpoints for survival, safety, tolerability, and toxicity – all of which are important outcomes.

This trial will use adaptive sample size, requiring 36 CSF culture positive participants and enrolling up to 50 total participants with cryptococcal meningitis.

Note on subjects with previous history of cryptococcal meningitis

Subjects with a previous history of prior, known cryptococcal meningitis will be included in the trial as long as they did not receive >2 days of 5-FC during their previous treatment. The rationale for this is that most patients in Uganda would have previously been treated with fluconazole during induction therapy and relapse is highly associated with fluconazole resistance.³⁴ These patients may still benefit from an induction regimen that includes 5-FC and would be ideal candidates for this therapy when it becomes more widely available.

****Note on laboratory exclusion criteria***

Subjects can be enrolled into the study before the laboratory data is available. Labs should be sent on enrollment and should be available within 72 hours. Subjects meeting laboratory exclusion criteria will be withdrawn from the study (See section 5.6).

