The control cohort will be drawn from the AMBITION trial that was conducted partly in Uganda.⁴³ This was a randomized clinical trial that evaluated single high-dose amphotericin B (10 mg/kg) with fluconazole (1200 mg/day) and flucytosine (100 mg/kg/day) for 2-week induction therapy of cryptococcal meningitis compared to standard amphotericin deoxycholate (1 mg/kg/day) with flucytosine (100 mg/kg/day). The trial enrolled participants who were HIV positive with a first episode of cryptococcal meningitis diagnosed by cryptococcal antigen or India ink staining. Participants were excluded if they were pregnant, had already taken amphotericin or fluconazole for >48 hours, had a previous serious reaction to the study medications or were taking a medication that would be contraindicated with the study medications. In Uganda, the trial enrolled 163 participants in the control arm and 164 in the intervention arm for a total enrollment of 327 Ugandan participants. The control cohort will be drawn from Ugandan participants. If IV liposomal amphotericin B is used in the investigational cohort then they will be drawn from the intervention arm. If IV deoxycholate amphotericin B is used in the investigational cohort then they will be drawn from the control arm. We will compare the EFA of all the control participants to the interventional participants using multivariate mixed linear regression, adjusting for confounding factors such as CD4+ count, GCS<15 or not, prior exposure to ART or not and other important clinical factors. We will also compare 10-week survival in the

interventional and control cohorts, using multivariate Cox regression, adjusting for the same clinical factors as the mixed regression model.

This 2018 and 2022 WHO recommended regimen is based on a phase III randomized clinical trial demonstrating that:

- i) 1 week of IV AMB had equivalent survival as 2 weeks of IV AMB;²
- ii) 1 week of IV AMB combination therapy was less toxic than 2 weeks of IV AMB;² and
- iii) Adjunctive flucytosine had superior survival to adjunctive fluconazole.²

A DSMB review by the full committee will occur after 10 participants have been enrolled with >2 weeks of accrued data. A local Ugandan community member will be invited to attend open DSMB meetings. The DSMB safety reports will be submitted to the IRBs and regulatory authorities.

Timing of ART Initiation or Switch.

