5.6 Study Withdrawal

By consenting to the trial, participants are consenting to receiving the study treatment, study follow-up and study data collection. However, a study subject may discontinue from further ongoing study participation at any time if:

- Subject wishes to voluntarily withdraw.
- Fulfillment of early withdrawal criterion: absolute neutrophil count < 500 x 10⁶ cells/L, thrombocytopenia < 50,000 x10⁶ cells/L, or renal creatinine clearance < 20 mL/minute

- Any unacceptable toxicity or adverse event (ie. Development of severe renal dysfunction or leukopenia on treatment).

Subjects are free to withdraw from participating in the study at any time upon request. If voluntary withdrawal occurs, the subject will be asked to complete an end-of-study evaluation and be given appropriate care under medical supervision until the symptoms of any AE resolve or the subject's condition becomes stable. The patient will be offered ongoing follow-up care at the site outpatient HIV clinic or referred to a clinic of their choice if withdrawn from the study. Participants who withdraw from Mulago hospital will not be contacted after withdrawal of consent.

Subjects may discontinue the study intervention (as per Section 5.5) and remain in the research study for safety monitoring and assessment of endpoints, receiving standard of care therapy.

Subjects withdrawing from the study will be recommended to receive standard of care therapy.

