7.2 Enrollment

At the time of initial hospital presentation, participants presenting with suspected CM will be evaluated by the study team. An LP will be performed by the study team per standard of care for evaluation of a patient with signs of meningitis (Section 8.2). For women of childbearing potential, a urine pregnancy test will be administered.

Study staff will verbally screen for inclusion/exclusion criteria when introducing the patient information sheet at the start of the informed consent process. Diagnostic CSF analysis includes:

- CSF white cell count
- CSF protein
- Quantitative fungal culture⁵⁹
- Cryptococcal antigen (CrAg) by lateral flow assay⁵⁴
- CSF storage for possible PK studies or future immunology assays

Documented cryptococcal meningitis will be defined as either CSF fungal culture positive for *Cryptococcus* species and/or CSF CrAg positive. As trial enrollment will be within the first 48 hours after diagnosis, CSF CrAg results will be used as the inclusion criteria, as the CSF fungal culture takes >48 hours. CSF analysis performed at the local approved microbiology laboratory. The purpose of the first lumbar puncture is to make the etiologic diagnosis of meningitis (an inclusion criterion) and collect baseline CSF parameters and CSF specimens prior to antifungal therapy. As with every LP in this trial, CSF will be sent for quantitative cryptococcal cultures.

If the participant meets all inclusion/exclusion criteria and completes the informed consent process by signing the informed consent document, they will be considered eligible for enrollment into the study.

A physician assessment at this time will include:

- Complete medical history
- Vital Signs
- Complete physical examination

At enrollment, current signs/symptoms occurring must be recorded. All signs/symptoms must be recorded on CRFs at time of enrollment, so that new AEs may be correctly assessed and documented on an ongoing basis. Pre-existing Grade 3-4 events are commonly expected among participants at study entry and will likely include: fatigue, weight loss, anorexia, nausea, vomiting and neurologic (behavior/alterated mental status/cognitive/headache) abnormalities.

Within \pm 72 hours of enrollment, baseline laboratories will be collected for:

- Complete blood count (CBC)
- Chemistry panel (e.g., Na, K, creatinine at minimum, with calculated creatinine clearance)
- CD4 T cell count, as possible
- HIV RNA (viral load)
- Liver function tests (ALT, T-bilirubin)

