- Specimen Storage
- Peripheral blood mononuclear cells (PBMCs) – Kampala only (optional)

We expect that most patients that undergo screening will already have an HIV diagnosis. In the event of unknown HIV-status, HIV screening will be the rapid test per the current hospital protocol of universal HIV testing of all hospitalized patients (i.e. opt-out). Additional

screening for AIDS-related OIs may occur as per standard medical practice, particularly for tuberculosis.

Study days are numbered starting from the first day of diagnosis (Day 1 = the day the subject receives first dose of IV AMB therapy). The format of the visit code will be 'xx.y', where 'xx' is the study week, and 'y' is the study day of the corresponding week. For example, day 1 of the study is the day the subject received the first dose of IV AMB and will be denoted '00.1'. Day 10 of the study (1 week and 3 days) would therefore be denoted '01.3'.

Participants may receive up to 2 days of standard dose 5-FC and remain eligible, so as to allow participants adequate time for their decision on whether to participate in the research project as well as to allow for weekends or holidays. The number of 5-FC doses should start with the first investigational dose received, and the schedule of events adjusted accordingly.

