7.5.1 Early Termination

In case of early termination, a reason for study termination will be documented. Reasons for early termination include withdrawal of consent, death, transfer of care, or loss-to-follow-up. An attempt will be made to schedule a termination visit. Assessment and laboratory evaluations for an early termination visit will be the same as the Week 18 visit.

If subjects withdraw from the study, they remain eligible for ART per national guidelines. Persons withdrawing will be encouraged to continue to receive ART from the outpatient clinic or referred to a clinic of their choice for ongoing HIV care and management of CM.

Subjects enrolled in the study but choosing to leave the hospital early against medical advice will continue to participate in the study if they wish. Additional phone calls by study personnel will encourage the subject to seek follow up HIV care and to rejoin the trial per the ongoing schedule of events. Assessment of vital status will continue via telephone calls at a minimum, unless consent is completely withdrawn.

All analysis is by intention to treat, thus anyone voluntarily discontinuing study participation must have a specific request made to them of whether continued collection of vital status (dead / alive) via an 18-week visit or a phone call at a minimum is allowable.

For persons involuntarily defaulting from study participation due to circumstances beyond their individual control (e.g., moving residence due to financial reasons, etc.), appropriate referral to local HIV-care will be arranged and a request made for a Week 18 visit. Actual transport expenses may be reimbursed in these rare occasions with prior approval of the site PI. Alternatively, phone visits may be conducted as outpatient to assess interval history and vital status.

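### Withdrawal from the study on laboratory values that may already be on-treatment can end follow-up of participants selected by a safety outcome, contrary to the all-enrolled intention-to-treat statement

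*Combined protocol and SAP*

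**What the plan says.** All references are to the combined protocol and SAP.

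- **Section 5.1, note on laboratory exclusion criteria.** Participants may be enrolled before laboratory data are available. "Labs should be sent on enrollment and should be available within 72 hours". Then: "Subjects meeting laboratory exclusion criteria will be withdrawn from the study", with a pointer to section 5.6.
- **Section 7.2.** The sampling window is wider than the note suggests: within plus or minus "72 hours of enrollment, baseline laboratories will be collected for" blood count and creatinine, among others. The same section states: "Participants may receive up to 2 days of standard dose 5-FC and remain eligible". Section 5.2.2 gives the same 2-day allowance.
- **Section 5.6.** Here the wording is permissive: "a study subject may discontinue from further ongoing study participation at any time if" one of several conditions holds. One condition repeats the neutrophil, platelet and creatinine-clearance limits, with no time restriction. Another is "Any unacceptable toxicity or adverse event (ie. Development of severe renal dysfunction or leukopenia on treatment". Section 5.6 also allows a participant to stop the intervention and stay in the study for safety monitoring and endpoints. Sections 5.5 and 9.8 allow the same.
- **Analysis set.** The synopsis (Phase II Statistical Design Rationale) includes everyone enrolled. Section 7.5.1 says "All analysis is by intention to treat", and sections 7.5 and 11.1 agree.
- **Controls.** Section 4.1 summarises the AMBITION exclusions: "Participants were excluded if they were pregnant, had already taken amphotericin or fluconazole for >48 hours", plus earlier serious drug reactions and contraindicated medicines. It mentions no laboratory limits and compares EFA with all control participants. The synopsis (Phase II Study Design) instead describes controls as selected and weighted by eligibility criteria, baseline characteristics and therapy.

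**The concern.** A rule that removes people from a study after enrolment is harmless to inference only if the reason is fixed before treatment and follow-up is kept. Neither is assured here. The trigger can be measured after amphotericin and 5-FC have begun, and it concerns the toxicities the trial sets out to compare. Grade 3 and Grade 4 haematological events by 2 weeks are DOOR ranks (section 11.5), and Grade 3–5 laboratory abnormalities over 2 weeks are named the key safety endpoint (section 11.6).

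Departure on such a value is informative. What may be lost is what comes afterwards: later serious adverse events, death by Week 18, and the follow-up lumbar puncture without which EFA cannot be calculated (section 11.4.1). Nothing in the plan describes a matching removal of AMBITION controls on laboratory values taken after their treatment began.

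**Working it through.** **1. Can the triggering value be on-treatment?** Up to 2 days of 5-FC may precede enrolment (sections 5.2.2, 7.2), and amphotericin and 5-FC start once the diagnosis is confirmed (section 5.3.1). If the sample is sent at enrolment, as the note in 5.1 asks, it can follow up to 2 days of treatment. If it is drawn at the end of the section 7.2 window, it can follow 2 days + 72 hours = about 5 days. No section separates a pre-treatment value from an early on-treatment one.

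**2. What happens to a participant who crosses a limit?**
- Enrolment laboratories, 5.1 note: leaves the study, mandatory.
- Any time, 5.6: may leave the study.
- Any time, 5.5, 5.6 and 9.8: may stop the drug and remain.

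The same event has several routes and no rule for choosing among them.

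**3. Is follow-up protected after a laboratory withdrawal?** Section 7.5 lists completion, withdrawn consent, death, transfer of care and loss to follow-up as termination reasons; laboratory withdrawal is absent. In section 7.5.1 the vital-status request is written for voluntary discontinuation. Separate provisions cover leaving hospital against advice and circumstances such as moving home. None names laboratory withdrawal. Section 11.6 only summarises withdrawals.

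**4. DOOR.** Taking the section 11.5 list as running from best to worst, loss to follow-up (e) lies below Grade 3 and 4 haematological events (c, d) and above serious adverse events (f) and death (g). The plan does not say whether a laboratory withdrawal goes to (e). If it did, a participant with only a Grade 4 value would be ranked worse than the observed event, and one who later died unseen would be ranked better than death.

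**5. The plan's sample size.** The target is 36 culture-positive participants from up to 50 enrolled (section 5.1), with 10–15% culture-negative. 36/0.90 = 40 and 36/0.85 = 42.4, so 43. The cap of 50 implies a total loss of 1 − 36/50 = 28%, with no breakdown, so it can be neither reproduced nor called wrong. Assume a proportion w is withdrawn independently of culture status and without an EFA. Those left are 50 × (1 − culture-negative share) × (1 − w), with the share at 15% and then 10%:
- w = 5%: 40.4 to 42.8
- w = 10%: 38.25 to 40.5
- w = 15%: 36.1 to 38.25
- w = 20%: 34.0 to 36.0

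The target survives to about 15% withdrawal. The issue is bias, not numbers.

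**6. Effect on mortality.** Section 9.2.1 expects deaths from cryptococcal infection in up to 20% of participants; take m = 0.20. The documents give no withdrawal rate and no risk for those withdrawn, so both w and the risk ratio RR (withdrawn against retained) are assumptions. If deaths after withdrawal are not seen, retained mortality is m / (1 − w + w × RR).

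| w | withdrawn of 50 | RR 1 | RR 2 | RR 3 |
|---|---|---|---|---|
| 5% | 2.5 | 20.0% (0) | 0.20/1.05 = 19.0% (−1.0) | 0.20/1.10 = 18.2% (−1.8) |
| 10% | 5.0 | 20.0% (0) | 0.20/1.10 = 18.2% (−1.8) | 0.20/1.20 = 16.7% (−3.3) |
| 15% | 7.5 | 20.0% (0) | 0.20/1.15 = 17.4% (−2.6) | 0.20/1.30 = 15.4% (−4.6) |

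At RR 2, about 1.0, 1.8 and 2.6 of 10 expected deaths would go unseen.

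**7. Is the range of w plausible?** Appendix A reports, in 177 subjects of another trial, 12 + 12 = 24 Grade 4–5 neutropenia events (0.14 per subject) and 4 + 13 = 17 Grade 3–5 thrombocytopenia events (0.10 per subject). These are events, not persons, on a regimen of amphotericin and fluconazole. They show only that 5–15% is not extreme. The 20% transient renal insufficiency in section 9.2.2 is not a rate of crossing the creatinine-clearance limit and is not used.

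**The case against.** Several stronger readings are tempting, and the documents do not support them.

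- **That the plan removes toxicity and deaths from the analysis.** No section drops withdrawn participants, and the synopsis says everyone enrolled is included. The triggering value itself is kept, because laboratory events are graded from the database (sections 9.6, 9.7.1). What can be lost is what follows it.
- **That on-treatment toxicity must lead to withdrawal.** Section 5.6 says a participant may leave, and itself offers the option to stop the drug and remain. Only the 5.1 note is mandatory, and it concerns enrolment laboratories.
- **That baseline samples are usually on-treatment.** The note asks for samples at enrolment, and the section 7.1 schedule shows blood count and creatinine at screening too. The wording makes a late sample possible; nothing suggests it is typical.
- **That the limits apply to one cohort only.** The synopsis weights control selection by eligibility criteria, which could carry the baseline limits across, and section 11.3 defers historical-control detail to an SAP. Against this, section 4.1 uses all controls and lists no such limits. The question is unsettled for pre-treatment values. For post-treatment values, nothing describes a parallel removal.
- **That the bias must favour the low dose.** Unseen deaths would, but a loss-to-follow-up rank for a participant with only a haematological event would count against it.

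Secondary endpoints are also declared mainly descriptive (section 11.7). These points narrow the concern. They do not supply a follow-up rule or settle which section governs.

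**Conclusion.** The concern holds in a limited form. One rule requires, and another permits, participants to leave the study on laboratory values that may have been measured after treatment began and that overlap the safety and DOOR endpoints. This conflicts with the all-enrolled intention-to-treat statement, and no provision secures follow-up afterwards.

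The size cannot be known from the documents. Under the stated assumptions (20% mortality, 5–15% withdrawn, later deaths unseen) the understatement of mortality runs from 0 at equal risk to 4.6 points at 15% withdrawn and three times the risk. The primary sample size is not threatened up to about 15% withdrawal. The change should be made before follow-up is lost, because it may not be recoverable at analysis.

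**What to change.** 1. Reconcile the 5.1 note with the synopsis and sections 5.5, 5.6 and 9.8 so that a laboratory trigger after enrolment does not end study follow-up. Whether and when study drug is stopped or changed is for the sponsor to settle across these sections; no rule is proposed here.
2. Define the intention-to-treat set in section 11.1 as all enrolled participants.
3. Continue endpoint and vital-status follow-up to Week 18 unless consent is withdrawn, and extend sections 7.5 and 7.5.1 to cover these participants.
4. Distinguish samples drawn before any 5-FC or amphotericin, which bear on eligibility, from later samples, which are safety outcomes. A cut-off at the first low-dose 5-FC dose is not enough, since up to 2 days of standard-dose 5-FC may come first.
5. State the DOOR rank for a participant who meets a laboratory trigger.
6. Apply the same pre-treatment laboratory filter to AMBITION baseline values when selecting controls, and add a sensitivity analysis with the filter applied to both cohorts and lifted from both.

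The cost is wording in a few sections and follow-up of a small number of participants at visits already scheduled; visits beyond Week 6 may be by phone (section 7.4.1). The target of 36 need not change: with no one withdrawn, 42.5 to 45 culture-positive participants are expected from 50.
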